### **10.2 Methods of Measurement**

Conventional CT and MRI should be performed with cuts of 5 mm or less in slice thickness contiguously. If CT scans have slice thickness greater than 5 mm, the minimum size for a measurable lesion should be twice the slice thickness. Spiral CT should be performed using a 5-7 mm contiguous reconstruction algorithm. This applies to tumors of the chest, abdomen and pelvis.

Baseline documentation of "Target" and "Non-Target" lesions:

#### Target Lesions

All measurable lesions up to a maximum of 2 lesions per organ and 5 lesions in total, representative of all involved organs, should be identified as target lesions and recorded and measured at baseline. Target lesions should be selected on the basis of their size (lesions with the longest diameter), be representative of all involved organs, but in addition should be those that lend themselves to reproducible repeated measurements. It may be the case that, on occasion, the largest lesion does not lend itself to reproducible measurement in which

circumstance the next largest lesion which can be measured reproducibly should be selected. A sum of the diameters (longest for non-nodal lesions, short axis for nodal lesions) for all target lesions will be calculated and reported as the baseline sum diameters. If lymph nodes are to be included in the sum, then only the short axis is added into the sum. The baseline sum of the diameters will be used as reference to further characterize any objective tumor regression in the measurable dimension of the disease.

### Non-target Lesions

All other lesions (or sites of disease) including any measurable lesions over and above the 5 target lesions should be identified as non-target lesions and should also be recorded at baseline. Measurements of these lesions are not required, but the presence or absence of unequivocal progression of each should be noted throughout follow-up.

## **10.3 Response Criteria**

Evaluation of target lesions

**\*Complete Response (CR):**

Disappearance of all target lesions. Any pathological lymph nodes (whether target or non-target) must have reduction in short axis to < 10 mm. For patients with > 90% Partial Response defined as at least a 90% decrease in the sum of the LD of target lesions, taking as reference the baseline sum LD sustained for greater than one year will be scored as a CR (maximal patient benefit), given the difficulty of evaluating lesions in some instances.

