## **10.0 DETAILED RESPONSE ASSESSMENT (also see 6.4)**

Response will be defined by NCI's Response Evaluation Criteria in Solid Tumors (RECIST) 1.1.

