**Table 7. Response Criteria**

Target lesions	Non-Target lesions	Overall response
CR	CR	CR
CR	Incomplete response/SD	PR
PR	Non-PD	PR
MR	Non-PD	MR
SD	Non-PD	SD
PD	Any	PD
Any	PD	PD
Any	Any	PD

Patients with a global deterioration of health status requiring discontinuation of treatment without objective evidence of disease progression at that time should be classified as having "symptomatic deterioration". Every effort should be made to document the objective progression even after discontinuation of treatment. In some circumstances it may be difficult to distinguish residual disease from normal tissue. When the evaluation of complete response depends on this determination, it is recommended that the residual lesion be investigated (fine needle aspirate/biopsy) to confirm the complete response status.

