### **10.4 Confirmation**

The main goal of confirmation of objective response is to avoid overestimating the response rate observed. To be assigned a status of PR or CR, changes in tumor measurements must be confirmed by repeat assessments that should be performed no less than 4 weeks after the criteria for response are first met. In the case of SD, follow-up measurements must have met the SD criteria at least once after study entry at a minimum interval (in general, not less than 6-8 weeks) that is defined in the study protocol.

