### 13.2 Analysis Plan

The data will be analyzed for response, overall survival and other endpoints, as described in this section; data will only be analyzed as specified in Section 14.3.1 to ensure the toxicity of IL-2+HCQ is not unexpectedly high. All analyses will be performed using the most recent versions of SAS and/or R available.

- 13.2.1.** *Estimate the proportion of patients with metastatic RCC treated with IL-2 combined with hydroxychloroquine at 600mg/d who experience a clinical complete response.* Response is defined in Section 10.3. The probability of each category of response will be estimated. Secondary analyses will employ cumulative logit regression for increasing levels of response, with adjustment for demographic and clinical covariates. All point estimates will be accompanied by appropriate 95% confidence intervals.
- 13.2.2.** *Compare the response, overall survival and time to progression of patients with metastatic RCC treated with IL-2 combined with hydroxychloroquine to the published response of patients treated with high dose IL-2 alone.* Logistic and proportional hazards (Cox) regression will be used to compare clinical response, and OS and PFS, respectively, to examine the effect of HCQ on the efficacy of IL-2. Formal tests of non-inferiority are beyond the scope of this Phase II study, and these secondary analyses are not statistically powered.
- 13.2.3.** *Characterize the toxicity of IL-2 combined with hydroxychloroquine in patients with metastatic RCC: number of doses of IL-2 administered during the first course of therapy; toxicity after the scheduled 9th dose of IL-2; frequency of grade III and IV or unexpected or rare toxicities.* Number of doses, maximal toxicity grade and incidence of treatment-limiting toxicities (TLTs, as defined in Section 10.5) will be tabulated.

**13.2.4** *Evaluate the utility of known prognostic criteria for RCC patients on clinical outcome.* Prognosis is evaluated by whether the patient has 0, 1, or 2, or 3 or more of the following risk factors:

- lactate dehydrogenase (> 1.5 upper limit of normal)
- hemoglobin (< lower limit of normal)
- corrected calcium (>10mg/dL)
- Karnofsky performance status (< 80%)
- time from initial RCC diagnosis to start of interferon- $\alpha$  therapy of less than one year

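### Sections 10.3 and 11 disagree on where a lasting response of 90% or more is counted, so a strict CR rate is not clearly planned and the match to the ~8% benchmark is not shown

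*Combined protocol and SAP*

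**What the plan says.** - **Section 1.1**: the primary objective is to estimate the CR proportion at 600 mg/d of hydroxychloroquine.
- **Section 10.0**: "Response will be defined by NCI's Response Evaluation Criteria in Solid Tumors (RECIST) 1.1".
- **Section 10.3**, under "Evaluation of target lesions": CR is the disappearance of all target lesions, with nodes below 10 mm in short axis. A second route follows. A decrease of at least 90% in the sum of target-lesion diameters, "sustained for greater than one year will be scored as a CR (maximal patient benefit), given the difficulty of evaluating lesions".
- **Section 10.3, Table 7**: target CR with "Incomplete response/SD" in non-target lesions is an overall partial response (PR).
- **Section 10.4**: "To be assigned a status of PR or CR, changes in tumor measurements must be confirmed by repeat assessments", at least four weeks later.
- **Section 11**: each patient is assigned one category. CR is category 1. PR above 90% is category 2, with no condition on duration.
- **Section 13.2.1**: for the primary proportion, "Response is defined in Section 10.3", and "The probability of each category of response will be estimated".
- **Section 13.2.2**: the comparison with published high-dose IL-2 results is described by "these secondary analyses are not statistically powered".
- **Sections 13.3.2 and 13.4**: the historical CR rate is 8/95, or about 8%, and the design is motivated by doubling it. Section 2.3 reports the eight CRs without a CR definition.
- **Section 2.2**: in the 255-patient IL-2 series there were 17 CRs and 20 PRs, and 60% of the PRs had more than 90% regression.

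**The concern.** The analysis section sends the primary CR count to a definition wider than RECIST 1.1. Section 11 appears to keep some or all of the extra patients in a separate line. A patient with a 90% decrease held for more than a year is a CR under Section 10.3 but could be placed in category 2 under Section 11, and no sentence says which prevails.

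This is a single-arm estimation trial whose rate will be read against about 8%. If the wider definition is applied here and was not applied to the historical patients, part of any excess would come from scoring. The reader could not tell how much unless the strict and rule-based CRs are reported separately.

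**Working it through.** **1. The plan's own figure.** Section 13.4 gives an exact 95% interval of (0.07, 0.34) for 5/39. The Clopper-Pearson limits are the 2.5% quantile of Beta(x, n−x+1) and the 97.5% quantile of Beta(x+1, n−x). For x=5, n=39 they are 0.043 and 0.274. The printed interval does not reproduce. That is a separate matter, and the recomputed interval is used here.

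**2. Direction.** If Section 10.3 governs, every strict CR is also a Section 10.3 CR. The primary rate is therefore equal to or above the strict rate in the same patients. If Section 11 governs and a lasting response above 90% stays in category 2, category 1 is the strict rate and there is no effect.

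**3. Size per patient.**
- n=39 (accrual goal, Section 13.1): 1/39 = 2.6 percentage points.
- n=26 (first five plus 21 more at 600 mg/d, Section 2.18): 1/26 = 3.8 percentage points.

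**4. Illustration with one rule-based CR.** The 5/39 is the plan's own scenario. The 4/26 is a hypothetical count.

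| CRs under 10.3 | Rate (exact 95% CI) | Strict, if one is rule-based |
|---|---|---|
| 5/39 | 12.8% (4.3–27.4%) | 4/39 = 10.3% (2.9–24.2%) |
| 4/26 | 15.4% (4.4–34.9%) | 3/26 = 11.5% (2.4–30.2%) |

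**5. Bound from the one historical series that mentions such patients.** From Section 2.2:
- PRs with more than 90% regression: 0.60 × 20 = 12, all left as PR.
- CR rate as reported: 17/255 = 6.7%.
- If all 12 met the Section 10.3 rule: (17 + 12)/255 = 29/255 = 11.4%.
- Scaled to this trial: 12/255 × 39 = 1.8 patients at most.

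The range is 0 to 4.7 percentage points. The upper end needs all 12 to have held the decrease for more than a year, measured by diameter, with non-target disease cleared. The documents give none of this.

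**6. Comparability.** Neither Section 2.3, for the 8/95, nor Section 1.2, for the Proclaim source, says how a lasting 90% decrease was scored. Like-for-like scoring is neither shown nor refuted for those two sources.

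**7. What does not change.** Moving a patient from PR to CR leaves CR+PR unchanged. Table 8, as captioned, counts partial or complete responses, so its stopping boundary is unaffected.

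**The case against.** The rule is prespecified, visible and given a reason. The objective speaks of clinical complete response, there is no formal test against 8%, and the historical comparison is declared unpowered. All of that stands, and it is why the Section 10.3 rate can remain the primary estimate.

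Four stronger readings are tempting but not supported.

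- **That no strict CR rate is planned at all.** Section 11 lists PR above 90% separately, and Section 13.2.1 estimates each category. If Section 11 governs, a strict rate would result. The documents support only that one is not clearly planned.
- **That a rule-based CR can bypass persisting non-target disease.** The rule sits under target lesions. Table 7, read after it, turns target CR with incomplete non-target response into PR. One confirming sentence is enough.
- **That duration beyond a year cannot be documented.** Scheduled CTs end a year after the final course, so a decrease first seen at a post-treatment scan cannot be shown on them to last longer than a year. But Section 6.4.2 allows review of routine scans afterwards. A decrease seen at week 8 can also be followed for more than a year on scheduled CTs, even after one course (12 + 52 − 8 = 56 weeks).
- **That the scoring rule could readily explain the whole excess over 8%.** This needs two of the five CRs in the plan's scenario to be rule-based (3/39 = 7.7%), which is above the bound of 1.8 per 39 in step 5. That bound may itself be generous. Section 2.2 describes tumor burden in cm². If regression was also measured by area (an assumption), uniform shrinkage of 90% in area is a diameter decrease of 1 − √0.1 = 68%, and some of the 12 would not qualify.

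It is also fair to say that a strict RECIST 1.1 rate is not proven like-for-like with 8/95 or Proclaim. It removes this trial's added route to CR from the comparison. It does not settle what the sources did.

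**Conclusion.** The point holds as an inconsistency of definition with a one-directional effect, of minor to moderate weight. Sections 10.3 and 11 do not agree on where a lasting response of 90% or more is counted. If Section 10.3 governs, as Section 13.2.1 indicates, the primary CR rate is equal to or above a strict rate in the same patients, by 2.6 percentage points per rule-based CR at n=39 or 3.8 at n=26. The total may be nil, because the number of such patients cannot be predicted from the documents.

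A reader might infer that the trial's rate is biased upward against the ~8% benchmark. The documents do not establish that. They show only that the 255-patient series left its regressions above 90% as PR, and that the definitions behind 8/95 and Proclaim are not given. Sampling error is also larger than the likely effect: with no rule effect, the chance of five or more CRs in 39 is already 20% at a true rate of 8%. What is affected is how the primary estimate and the unpowered historical comparison are read.

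**What to change.** - **Section 13.2.1**: keep the Section 10.3 rate as the prespecified primary if wished. Beside it, report the strict confirmed RECIST 1.1 CR rate with its exact 95% interval, and the number of CRs scored by the 90% rule.
- **Section 13.2.2 and any reading against ~8%**: use the strict rate unless the source is shown to apply the same rule, and note that the source's CR definition is not given.
- **Sections 10.3 and 11**: state which category a response of 90% or more enters before and after one year.
- **Section 10.3**: add one sentence confirming that Table 7 applies to rule-based target CRs, so that persisting non-target disease gives PR.
- **Sections 6.4.2 and 10.3**: state that routine scans obtained in follow-up may document the one-year duration once scheduled CTs have ended.

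The cost is a few sentences and one or two tabulated lines. No new data are needed, and the primary definition does not change after patients have been treated. The downside is that the CR rate set against the benchmark may be lower.

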**\*Partial Response (PR):**

At least a 30% decrease in the sum of the LD of target lesions, taking as reference the baseline sum LD

**\* Minimal Response (MR):**

At least a 20% decrease in the sum of the LD of target lesions, taking as reference the baseline sum LD

**\*Progressive Disease (PD):**

At least a 20% increase in the sum of the LD of target lesions, taking as reference the smallest sum LD recorded since the treatment started. In addition to the relative increase of 20%, the sum must also demonstrate an absolute increase of at least 5 mm.

**\* Stable Disease (SD):**

Neither sufficient shrinkage to qualify for PR nor sufficient increase to qualify for PD, taking as reference the smallest sum LD since the treatment started. Note: a change of 20% or more that does not increase the sum of the diameters by 5 mm or more is coded as SD.

Evaluation of non-target lesions

**\* Complete Response (CR):** Disappearance of all non-target lesions and normalization of tumor marker level. All lymph nodes must be non-pathological in size (<10 mm short axis)

**\* Stable Disease (SD):** Persistence of one or more non-target lesion(s) or/and maintenance of tumor marker level above the normal limits

**\* Progressive Disease (PD):** Appearance of one or more new lesions and/or unequivocal progression of existing non-target lesions. Although a clear progression of "non target" lesions only is exceptional, in such circumstances, the opinion of the treating physician should prevail and the progression status should be confirmed later on by the review panel (or study chair).

### **Evaluation of best overall response:**

The best overall response is the best response recorded from the date of first protocol treatment until disease progression/recurrence (taking as reference for PD the smallest measurements recorded since the treatment started). In general, the patient's best response assignment will depend on the achievement of both measurement and confirmation criteria.

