### 1.1 Primary:

1. Estimate the proportion of patients with metastatic RCC treated with IL-2 combined with hydroxychloroquine at 600 mg/d who experience a clinical complete response.

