Follow-up data on these patients has now been accumulated through June 2010, with a median follow-up of over 10 years. Although some late relapses are still being observed, the response duration curve appears to have leveled off after the 30 month time point and 60% of complete responders remain in remission. In addition, 4 PRs who underwent surgical resection of residual disease while still in response remain alive and disease-free at a minimum of 65+ months. Therefore, many CRs remaining free from progression for more than thirty months and those PRs resected to NED after a response to high-dose IL-2 are unlikely to progress and may actually be cured. Thus, although the response rate to high-dose bolus IL-2 is modest, it can produce meaningful benefit in a small proportion of patients. Means to enhance this response are clearly in order.

The High Dose Aldesleukin "Select" trial was conducted to prospectively assess the ability of histologic, immunohistochemical and other pathologic tumor features to predict overall response rate and other outcomes (McDermott et al. 2011). This study enrolled 123 patients between November 2006 and July 2009, at many of the same Cytokine Working Group Institutions participating in the present study. Patients received high dose aldesleukin at a standard dose and schedule, and with standard recommendations for treatment modification for toxicity (Schwartzentruber 2001). The High Dose Aldesleukin "Select" study therefore represents a contemporaneous population of patients with similar baseline characteristics and aldesleukin treatment with which to compare to the current study with regard to outcomes and toxicity."

In that trial, overall response rate was 25% by independent review (95% CI 17.5-33.7) and 28% by investigator review (as to be performed in this study) (95% CI 20.5-37.3%). The distribution of MSKCC 2002 risk was 19/70/11% (Good/Int/Poor). Median PFS was 4.3 months (95% CI 2.5-4.7 mo) (comparable to prior studies where about half the patients progressed on the first scan). As seen previously, there was a "tail" of durable progression-free survival (PFS rate at 3 years was 11%). Median overall survival was 42.8 months (95% CI 35.6-51.9 months). Median duration of response was 20.6 months (CI 6.9-42.7 mo)

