### **6.4 Response Assessment/ Duration of Therapy**

Patients will undergo CT scans at week 8 and week 12 (+/- 1 week) following initiation of IL-2 therapy and then after each course (every 10-12 weeks). After the final course (week 36), patients will undergo CT scan evaluation every 12 weeks (+/- 2 weeks) for up to one year or until tumor progression (whichever comes first). If additional scans are performed for clinical reasons, the study schedule may be altered to perform the requisite scans at a more acceptable time point. The change in timing of study scans must be approved by the local PI and documented. For patients who have not shown progression at the end of one year, response will be captured during follow-up for survival (explained below).

Patients with evidence of tumor shrinkage with all lesions measurable and evaluable may receive up to 3 courses of IL-2 therapy. Course 2 will start on or within 2 weeks following day 85 and follow the same schedule as in Course 1. Course 3 can start within 2 weeks of completion of Course 2. Patients not receiving IL-2 during course 2 with tumor shrinkage by week 24 can receive a 2nd course of IL-2 beginning within 2 weeks of week 25.

Patients with no evidence of progression by RECIST 1.1 criteria may receive continued treatment with hydroxychloroquine through one year of initiation of HCQ treatment (Day -14) or until disease progression.

Tumor response will be assessed by the NCI’s Response Evaluation Criteria in Solid Tumors (RECIST) 1.1 guidelines. Patients will undergo tumor evaluation with physical exam and CT scans at week 8 (+/- 1 week) and week 12 (+/- 1 week), then after each course (every 10-12 weeks). After the final course (week 36), patients will undergo CT scan evaluation every 12 weeks (+/- 2 weeks) for up to one year or until tumor progression (whichever occurs first). If additional scans are performed for clinical reasons, the study schedule may be altered to perform the requisite scans at a more acceptable time point. The change in timing of study scans must be approved by the local PI and documented. For patients who have not shown progression at the end of one year, response will be captured during follow-up for survival, which will be done on all patients via telephone contact and medical record review. Patients with progressive disease by RECIST 1.1 criteria will be taken off study.

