#### **6.4.2 Clinical Assessment and Duration of Therapy**

All patients will have blood tests and a thorough physical examination prior to each cycle of IL-2. Further therapy will be withheld until laboratory values and performance status return to within the eligibility criteria. IL-2 may be re-initiated once serum creatinine reaches  $\leq 1.8$  mg/dL (at the discretion of the treating physician).

Both responding and non-responding patients will be followed until death or final closure of the study. After the final course of treatment, follow-up procedures will be performed every 3 months (+/- 2 weeks) for up to one year or until disease progression (whichever occurs first). Follow-up procedures will include CT scan, routine laboratory tests, and physical examination. Subjects will then be followed for survival by telephone contact and medical record review every 3 months for one year following the time of disease progression or after one year off of treatment, then every 6 months for the next two years, then annually until death. A window of +/- 2 weeks is permitted. This will include review of any routine procedures performed as part of the patient's standard care (e.g., routine scans, physical examinations, laboratory exams, etc.). Attention will be paid to the time of disease progression and time of initiation of alternate therapies.

In the absence of treatment delays due to adverse events, treatment may continue for up to 3 courses per protocol or until one of the following criteria applies:

- Disease progression (see section 10.0),
- Intercurrent illness that prevents further administration of treatment,
- Treatment-related toxicities (see section 9.5),

- Subject decides to withdraw from the study, or is non-adherent,
- Subject becomes pregnant or begins breast-feeding,
- General or specific changes in the subject's condition rendering the subject unacceptable for further treatment in the judgment of the investigator.

Patients discontinued from the treatment phase of the study for any reason will be evaluated ~30 days (28-42 days) after the decision to discontinue treatment.

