### **10.8 Progression-free Survival**

Progression-free survival (PFS) is defined as the time from date of first protocol treatment until the date disease progression criteria are met (in responding patients progression criteria uses the reference of the smallest measurements recorded since the treatment started) or date of death from any cause, or is censored at date of last disease assessment for those who have not progressed.

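### The window for best overall response closes only at progression, so a complete response reached after non-protocol anticancer therapy or resection would count in the primary CR rate

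*Combined protocol and SAP*

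**What the plan says.** Section 1.1 sets the primary objective as the proportion of patients "who experience a clinical complete response" on IL-2 plus hydroxychloroquine at 600 mg/d.

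Section 10.3 fixes the period over which response is scored: "The best overall response is the best response recorded from the date of first protocol treatment until disease progression/recurrence". Target-lesion CR is "Disappearance of all target lesions", with a size limit for lymph nodes. Table 7 requires non-target CR as well before the overall category is CR, and 10.4 requires confirmation at least 4 weeks later. Section 10.3 also gives a second route: a target-lesion decrease of at least 90% "sustained for greater than one year will be scored as a CR (maximal patient benefit".

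Assessment does not end with treatment. Section 6.4.2 lists several reasons to stop without progression (intercurrent illness, toxicity, withdrawal, investigator judgment). Scans then continue every 3 months for up to a year or until progression. Section 6.4 adds: "For patients who have not shown progression at the end of one year, response will be captured during follow-up for survival".

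Section 6.4.2 asks for the relevant date: "Attention will be paid to the time of disease progression and time of initiation of alternate therapies". No definition in Section 10 and no analysis in Sections 11 or 13 uses it. PFS (10.8) ends at progression or death, "or is censored at date of last disease assessment for those who have not progressed". TTP (10.7) has the same censoring rule without death.

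**The concern.** The trial is meant to estimate what IL-2 plus hydroxychloroquine does. Followed literally, the response rule also credits that regimen with the effect of whatever comes next, provided RECIST progression has not been recorded first. Nothing in the treatment or ancillary-treatment sections bars other anticancer therapy before progression; 6.5.2 rules out only corticosteroids. Exclusion 3.2.xii concerns major surgery anticipated at entry and is not a rule for scoring response.

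Later treatment is foreseeable. Section 2.1 credits agents targeting VEGF and mTOR with longer survival, and Section 2.2 reports of the earlier IL-2 series that "4 PRs who underwent surgical resection of residual disease while still in response remain alive and disease-free".

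Misattributed responses can only raise the CR proportion. With few CRs expected, one patient moves the estimate visibly. Without a written rule, attribution would be decided after outcomes are known.

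**Working it through.** **The plan's own figures.** Section 13.4 gives a 95% exact interval of (0.07, 0.34), width 0.27, for 5 responses in 39. Clopper-Pearson limits for 5/39 are 0.043 and 0.274, width 0.231, so the printed interval does not reproduce. That is a separate matter and nothing here rests on it. Table 8 does reproduce: with a Beta(8, 87) prior and P(rate < 0.10) > 0.8, the stopping counts are 0, 1, 1, 1, 2, 2, 2 for n = 18 to 36.

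**Does the text let such a CR count?**

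1. Stopping without progression: allowed (6.4.2).
2. Other therapy or resection before progression: not barred, and not an end to assessment.
3. Scans and response capture: continue (6.4, 6.4.2).
4. All target and non-target disease absent and confirmed at 4 weeks or more: overall CR (10.3, Table 7, 10.4). Confirmation tests persistence, not cause.
5. Progression not recorded: the window is still open (10.3).

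For the second route, take the first scheduled scan at day 57 (Appendix B). More than a year of sustained response runs past day 57 + 365 = 422. Under the one-year limit in 6.4, hydroxychloroquine ends at day -14 + 365 = 351. On scheduled scans the requirement therefore extends at least 422 - 351 = 71 days beyond that limit.

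**Weight of one such CR.** The plan supports two denominators: 26 at 600 mg/d (5 + 21, Section 2.18) and 39 (13.1, 13.4).

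- n = 26: 1/26 = 3.8 points. Example: 2/26 = 7.7% (exact 95% CI 0.9-25.1) becomes 3/26 = 11.5% (2.4-30.2).
- n = 39: 1/39 = 2.6 points. Example: 3/39 = 7.7% (1.6-20.9) becomes 4/39 = 10.3% (2.9-24.2).

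**How many?** The documents give no rate, so this is a scenario.

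- Expected CRs at the historical rate in 2.3 (8/95): 26 x 8/95 = 2.19, leaving about 24 non-CR patients.
- Section 2.2 says about half of patients in prior studies progressed on the first scan. These leave the window, so about 12 remain.
- Assume 10-30% of the 12 start other therapy or are resected before progression, and 10-30% of those then meet confirmed CR: 12 x 0.10 x 0.10 = 0.12, to 12 x 0.30 x 0.30 = 1.08.
- As a share of 26: 0.12/26 = 0.5 points, to 1.08/26 = 4.2 points.

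Doubling the historical rate would mean 2.19 extra CRs in 26. The top of this range is 1.08/2.19 = 49% of that.

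**A documented anchor for resection.** Section 2.2 reports 17 CRs and 20 PRs in 255 patients, and 4 PRs resected while in response. 4/255 x 26 = 0.41 patients; 4/255 x 39 = 0.61. Had those four been scored CR, the series would read 21/255 = 8.2% instead of 17/255 = 6.7%. The four are those reported as still disease-free, so more may have been resected.

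**Futility count.** At 21 patients, Table 8 halts at 1 response and continues at 2, so one such response could reverse the decision. The caption counts partial and complete responses, whereas part of the text of 13.3.2 refers to complete responses. On the caption's reading, only a patient lifted from below PR changes the count. On the other reading, a PR upgraded to CR would too.

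**The case against.** The gap is one of omission: no sentence says that such responses count. Several features limit its size, and they stand. Overall CR needs every target and non-target lesion gone, plus confirmation. A CR after recorded progression is already excluded. Patients without progression may continue hydroxychloroquine for up to a year, so those with stable disease or PR after the last IL-2 course are not simply off therapy. Patients stopping for global deterioration have their own label under Table 7. The CR estimate carries an interval about 23 points wide for 5/39, against which one patient is small. None of this closes the window; it reduces how often the window matters.

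A reader might infer three stronger things that the documents do not support.

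- *Removing a target lesion makes the patient a CR.* It does not. Table 7 gives PR when non-target disease persists, and all target lesions must be gone. Section 2.2 still calls its resected responders PRs. That usage does not bind this trial, but it shows no intention to score them as CR.
- *The bias could equal the whole doubling sought.* Applying the same assumed rates to all 24 non-CR patients gives up to 24 x 0.30 x 0.30 = 2.16, about the 2.19 extra CRs hoped for. That ignores the half who progress at the first scan, and the rates have no source in the documents.
- *PFS and TTP are wrong for the same reason.* Following patients to progression (or death, for PFS) regardless of later therapy is a legitimate choice. The comparison with IL-2 alone is secondary and unpowered (13.2.2), and the documents do not say how the published comparator handled later therapy. The direction of any net bias there is unknown.

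**Conclusion.** The point holds for best overall response, and therefore for the primary CR rate and the responses fed to Table 8. As written, 10.3 would count a confirmed CR that follows non-protocol therapy or resection of all disease, and a PR above 90% kept beyond one year by later therapy. The effect on the CR rate is upward: 3.8 points per patient at n = 26 or 2.6 at n = 39. The likely number is small, about 0.1 to 1.1 patients in 26. That range rests on half of patients progressing at the first scan, as in prior studies, and on assumed 10-30% rates at each of two steps. The correction is cheap and worth making, but the trial's conclusions do not stand or fall on it.

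**What to change.** In 10.3 and 10.4, define best overall response as the best response up to the earliest of: progression or recurrence; start of any non-protocol anticancer therapy; or resection of, or radiation to, target disease. Apply the same limit to the confirming assessment and to the route that scores a PR above 90% as CR after more than a year. Later findings do not upgrade the category, and the patient stays in the denominator. Report PRs later resected to no evidence of disease separately, as PR. The Table 8 count should use the same definition.

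Leave 10.7 and 10.8 as they are. A PFS/TTP version censored at the last assessment before alternate therapy is an optional sensitivity analysis, not a correction.

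The cost is a few sentences. The alternate-therapy date is already followed under 6.4.2; the sponsor should make sure that the record includes resection and radiation. The downside is that the CR rate may be slightly lower, including when a CR first seen before later therapy is not confirmed until after it starts. The change governs scoring only and directs no care.
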